  2. **SACROCOLPOPEXY:** Sacrocolpopexy (SCP) is a common surgical treatment for symptomatic pelvic organ prolapse. While traditionally reserved for women with recurrent or vaginal vault prolapse SCP is becoming more common as the first surgical option for women with prolapse [7], because benefits are long-lasting with less than 5% of patients undergoing reoperation [8-11]. However, SCP is associated with an increased rate of intraoperative and post-operative complications compared to other surgical treatments [12], including bowel obstruction, mesh erosion, and venous thromboembolism. More recently minimally

invasive SCP (laparoscopic and robotic assisted) has become popular as it offers similar success rates with faster recovery, less pain, bleeding and cost [13-15]. Robotic surgery has several unique challenges including the absence of haptic feedback, and additional time required for setup. The mean time to complete robotic SCP is 79 minutes for attendings, and 76 minutes for trainees, with total operating time of 182 minutes for attendings, and 200 minutes for trainees [16].

[figure not shown]
3. **ANCHOR MESH FIXATION:** Anchor mesh fixation has been tested successfully in several applications. In laparoscopic incisional and ventral hernia repair, anchors have been used to fixate mesh. A systematic review [17] found four trials involving 207 surgeries comparing traditional suture mesh fixation to anchoring. Anchoring was associated with shorter operative time, less postoperative pain and similar rates of perioperative complications and hernia recurrence and shorter hospital stay. Both non-absorbable (titanium helical anchors) and absorbable anchors (Absorboanchor™, Covidien; Sucerestrap™, Ethicon) have been used with similar operating time, postoperative hospital stay, pain, morbidity and recurrence [18-21]. However longer term studies have reported more pain and erosion of non-absorbable anchors into hollow viscera [22] but perhaps higher recurrence rates with absorbable anchors[23]. Comparison of acute fixation strength of various attachment techniques has been performed, finding suture to provide the greatest strength and non-absorbable to provide more strength than absorbable anchors [24]. However, it is well known that mesh used for vaginal attachment is incorporated into the tissue after three months and the use of absorbable sutures for mesh attachment for sacrocolpopexy are commonly used [25].

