differences in analysis of outcome variables.

3. **STATISTICAL ANALYSIS OF OUTCOMES:** The primary endpoint for this study is the time of completion of mesh attachment. Statistical methods will include t-test or Mann Whitney U test for continuous variables, and chi-squared or Fischer's exact-test for categorical variables. We will collect the primary measure for outcomes of time of mesh attachment as a continuous variable. In addition we will use t-tests to evaluate the mean times of the different attachment approaches. Paired sample t test will be used to evaluate POP-Q values pre and postoperatively. Chi-squared test will be used to examine anatomic failures between the two. We will do risk analysis as appropriate using 95% confidence intervals odds ratios. For the analysis we will use SPSS 22.0.
4. **STUDY POWER AND SAMPLE SIZE:** A time of mesh attachment power calculation was performed using Power and Sample Size program (PS version 3.1.2). If suture mesh attachment interval =  $40 \pm 20$  mins [16,25], a 50% reduction with use of anchors is =  $20\text{mins} \pm 20$  mins. With 80% power and  $\alpha=0.05$ , 17 subjects will be needed for each arm. Anticipating a drop out of up to a 30% we will enroll 25 subjects in each group for a goal of at least 17 participants for each arm.

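### The odds ratio is the only planned effect measure for binary outcomes; with 17 to 25 women per arm it often cannot be estimated in the usual way if events are uncommon, and a risk difference with interval should replace it

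*Protocol*

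**What the plan says.** Protocol section 6.3 and SAP section 1.3 carry the same text on the analysis of outcomes. Three sentences concern binary outcomes:

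- Test in general: "chi-squared or Fischer's exact-test for categorical variables", with no rule for choosing between them.
- Test for anatomic failure: "Chi-squared test will be used to examine anatomic failures between the two".
- Effect measure: "We will do risk analysis as appropriate using 95% confidence intervals odds ratios". The sentence does not say which outcomes receive an odds ratio, and no other measure for binary outcomes appears anywhere.

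Neither document has a rule for zero cells, names an exact interval or mentions a risk difference.

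The numbers per arm come from section 6.4 and are driven by attachment time alone: "17 subjects will be needed for each arm", and "Anticipating a drop out of up to a 30% we will enroll 25 subjects in each group".

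Protocol section 2 states the secondary hypotheses that rest on these outcomes: comparable complication rates (i) and comparable surgical failure rates (ii). No expected rate and no margin is attached to either.

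**The concern.** An odds ratio needs events, and non-events, in both arms. If one arm has no events, the sample odds ratio is 0 or infinite. If neither arm has any, it is undefined. In both cases the usual interval, built on the log odds ratio and its standard error, cannot be computed. With 17 to 25 women per arm this is a foreseeable result for uncommon outcomes. Protocol section 5.3.iii lists several that could be uncommon: bowel, bladder or urethral injury, nerve injury, mesh exposure and reoperation. Anatomic failure joins them if its rate turns out to be low.

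A non-significant test does not support a claim that two rates are similar. An estimated difference with an interval is what shows how large a difference remains possible. Where the odds ratio fails, the plan names no substitute, so one would be picked after the data are seen.

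**Working it through.** **Inputs.** From the documents: 17 evaluable and 25 enrolled per arm, 1:1; alpha 0.05, taken as two-sided because the sidedness is not stated. Assumed: the true event rate p. The documents give none for failure or complications, so 2% to 20% is shown.

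**The plan's own figure.** For 40 versus 20 minutes with SD 20, the normal approximation gives n = 2 × (1.960 + 0.842)² × (20/20)² = 15.7, so 16 per arm. With the t distribution, power is 0.781 at 16 and 0.807 at 17, so 17 is right. For dropout, 17 / 0.70 = 24.3, so 25. Both stated figures reproduce. They say nothing about binary outcomes.

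**Chance of a zero cell.** An arm has no events with probability (1 − p)^n. With equal rates:

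P(at least one arm has none) = 1 − [1 − (1 − p)^n]²

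At p = 5%:

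- n = 17: 0.95^17 = 0.418, so 1 − 0.582² = 0.66.
- n = 25: 0.95^25 = 0.277, so 1 − 0.723² = 0.48.

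| Assumed rate in both arms | 17 per arm | 25 per arm |
|---|---|---|
| 2% | 92% | 84% |
| 5% | 66% | 48% |
| 10% | 31% | 14% |
| 15% | 12% | 3% |
| 20% | 5% | 1% |

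The chance that neither arm has an event is (1 − p)^(2n). At 5% it is 17% (17 per arm) and 8% (25 per arm). At 2% it is 50% and 36%.

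The result does not depend on equal rates. At 5% versus 15%, the chance of at least one empty arm is 1 − (1 − 0.418)(1 − 0.063) = 45% with 17 per arm, and 29% with 25.

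**What a risk difference gives.** Newcombe's interval combines the Wilson limits (l, u) of each arm. With d = p1 − p2:

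- lower limit = d − √[(p1 − l1)² + (u2 − p2)²]
- upper limit = d + √[(u1 − p1)² + (p2 − l2)²]

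For zero events the Wilson upper limit is z²/(n + z²): 3.84/28.84 = 13.3% at n = 25 and 3.84/20.84 = 18.4% at n = 17.

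| Events, arm A vs arm B | 17 per arm, difference in points (95% CI) | 25 per arm, difference in points (95% CI) |
|---|---|---|
| 0 vs 0 | 0 (−18.4 to +18.4) | 0 (−13.3 to +13.3) |
| 1 vs 0 | +5.9 (−13.2 to +27.0) | +4.0 (−9.7 to +19.5) |
| 2 vs 0 | +11.8 (−8.5 to +34.3) | +8.0 (−6.5 to +25.0) |

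Every one of these tables has an estimate and a finite interval.

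**The choice of test.** Enumerating all tables at 17 and 25 per arm for rates of 2% to 30%, the size of the uncorrected Pearson test never exceeded about 5.5%. With equal rates of 5% to 10%, Pearson and Fisher fall on opposite sides of 0.05 in 0.7% to 4.0% of trials.

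**The case against.** There are four serious counter-arguments.

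- **The rates may not be low.** This stands. The nearest figure is in Protocol section 3.2, "benefits are long-lasting with less than 5% of patients undergoing reoperation", but that is reoperation. Failure is defined anatomically in section 5.3.ii, and the complications in section 5.3.iii include bleeding, infection and urinary retention. A composite of any complication at 20% would rarely meet a zero cell. A reader might infer that 0 vs 0, 1 vs 0 and 2 vs 0 are the likeliest results. The documents do not support this: counting either arm as the empty one, those tables together have probability 41% at a 5% rate and 7% at 10%, with 25 per arm.
- **An odds ratio interval can still be had.** This stands in part. With one empty arm, an exact conditional interval exists but is open at one end: 1/25 vs 0/25 gives 0.03 to infinity, and 2/25 vs 0/25 gives 0.19 to infinity. The plan names no such method, and nothing is available for 0 vs 0.
- **The wording leaves latitude.** The odds ratio is planned only where appropriate. That permits omitting it but names nothing in its place.
- **The chi-squared test is not at fault.** This stands. A reader might infer that small expected counts invalidate the test for failure, or that the verdict will hinge on the test chosen. Pearson's size is not materially inflated here, the two tests seldom disagree at 0.05 under equal low rates, and for failure the plan fixes one test.

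**Conclusion.** The point holds for the effect measure and its interval, and only for uncommon binary outcomes. If the true rate is about 5%, roughly half (25 per arm) to two thirds (17 per arm) of trials would have no odds ratio with a standard interval. At 10% this is 14% to 31%, at 15% it is 3% to 12%, and by 20% it is 1% to 5%. These figures rest on assumed rates, equal in both arms and with independent patients; the documents supply none.

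The documents do not support saying that failure and complication rates in general will go unestimated, nor that the chi-squared test is invalid. The primary analysis and the sample size are unaffected. The matter is worth correcting because hypotheses i and ii depend on these outcomes and a better measure costs almost nothing.

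**What to change.** In Protocol section 6.3 and SAP section 1.3, replace the odds ratio sentence with a statement that every binary outcome (anatomic failure, complications, mesh exposure, reoperation) will be reported as counts per arm and a risk difference with a 95% confidence interval. Name the method in advance, either Newcombe or Miettinen-Nurminen.

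As a minor tidy-up, replace the general choice of two tests and the separate sentence on failure with one prespecified test for all binary outcomes. This is for consistency only. Fisher's exact test is conservative here: at a 10% rate and 25 per arm its actual size is 0.9%, against 4.9% for Pearson. Switching to it would not supply the missing estimate.

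The cost is a change of wording, with no new data, and a short calculation outside the standard SPSS cross-table. The intervals will be visibly wide: even with no events in either arm they reach about 13 points either way at 25 per arm and 18 at 17. They will therefore not by themselves establish that the rates are similar, and the report should say so.

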## 1. STATISTICAL ANALYSIS

1. PROCEDURES FOR DATA COLLECTION: Study participants will be closely observed by investigators to make sure that surgical appointments are set up. Data from preoperative period will be taken from the the EMR for the subject. Data for the primary outcome will be abstracted when the subject has their surgery.  
A Clinical report Form (CRF) will be used to collect history, physical examination, operation, operating times, technique, mesh attachment interval times, complications, and subsequent follow-up examination data. The investigators will input data into a pre-formatted spreadsheet. The spreadsheet will be maintained through the Kaiser Permanente San Diego research department on a password protected server and will be audited, reviewed and maintained by the investigators
  - i. Quality of Data: Data of the highest quality will be obtained from management data defined protocols for evaluating its accuracy (using source verification), completeness, accountability, and integrity.
  - ii. Completeness: the investigators will identify and complete any missing data.
  - iii. Accuracy: Errors in data will likely stem from errors in data entry. To minimize this, confirmation of data with a second source and random checks of data, and will be done. Error catching mechanisms in the Excel spread sheet and Access Database will be created with appropriate ranges and limits to help catch mistakes in data entry and allow for more accurate data entry.
  - iv. Auditing: Both sample and schedule-based auditing will be performed. Quarterly audits will be performed with random selection of 10% of the data to verify. Administrative audits will be done on a similar schedule to ensure compliance with Good Clinical Practices of the FDA.
  - v. Accountability: Accountability for data entry and data management will be with the investigators and statistical consultants.
  - vi. Integrity: mirrored hard drives, data back ups and storage on Kaiser Permanente San Diego server, will insure for data integrity.
2. ANALYSIS OF BASELINE DATA: Subject characteristics (measures and demographic information) collected at baseline will be compared across treatment groups, using either chi-square for categorical variables or t-test for continuous variables. We will examine these baseline characteristics for statistically significant differences between treatment groups, and use those that are identified for adjusted analysis correcting for these differences in analysis of outcome variables.
3. STATISTICAL ANALYSIS OF OUTCOMES: The primary endpoint for this study is the time of completion of mesh attachment. Statistical methods

will include t-test or Mann Whitney U test for continuous variables, and chi-squared or Fischer's exact-test for categorical variables. We will collect the primary measure for outcomes of time of mesh attachment as a continuous variable. In addition we will use t-tests to evaluate the mean times of the different attachment approaches. Paired sample t test will be used to evaluate POP-Q values pre and postoperatively. Chi-squared test will be used to examine anatomic failures between the two. We will do risk analysis as appropriate using 95% confidence intervals odds ratios. For the analysis we will use SPSS 22.0.

4. STUDY POWER AND SAMPLE SIZE: A time of mesh attachment power calculation was performed using Power and Sample Size program (PS version 3.1.2). If suture mesh attachment interval =  $40 \pm 20$  mins [16,25], a 50% reduction with use of anchors is =  $20\text{mins} \pm 20$  mins. With 80% power and  $\alpha=0.05$ , 17 subjects will be needed for each arm. Anticipating a drop out of up to a 30% we will enroll 25 subjects in each group for a goal of at least 17 participants for each arm.

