#### **4. OVERVIEW OF DESIGN**

1. **DESIGN DESCRIPTION;** This is a multi-site prospective, randomized, single-blind, 2 arms-parallel, clinical trial to evaluate the effect of absorbable anchor versus suturing of polypropylene mesh to the vaginas fibromuscular layer on the length of procedure for women undergoing SCP for POP. This effect will be studied using timing of the surgical procedure.
2. The study consists of a 1-year enrollment period concurrent with a 1-year single blinded period (the intraoperative data in which the patient is blinded to group assignment, but the surgeon/investigator is not), followed by a 6-month postoperative double blinded period (in which both the patient and surgeon/investigator).
3. During enrollment, patients who meet the inclusion and not the exclusion criteria and provide informed consent for participation will be assigned randomly to receive either absorbable anchor mesh fixation or suture mesh fixation.

Figure 1. Flowchart of study schema

4. **SCREENING PERIOD:** Subject will be screened for eligibility during a 1-year period that will include the preoperative office visit and preoperative unit visit. Office staff (research nurses, nurse practitioners, residents, fellows, attendings) will obtain written informed consent from participants as a part of enrollment. Standard physical exam measures (including POPQ) will be performed during the office visit. The suture allocation sealed envelope will be opened intra-operatively once it is certain the attachment of mesh will occur via a technique that is minimally invasive.
5. **STUDY PERIOD:** Study duration will be the 1 year concurrent period where surgeries are performed as well as the subsequent 6 months where postoperative visits occur. After randomization and surgery occurs subjects will follow up for a total of 6 months, with three visits, one at 6 weeks, one at 6 months. During these postoperative visits, a standard physical exam will be performed looking for signs of POP recurrence, mesh erosion, palpable suture, anchors, and other physical findings. The

patient will complete standardized questionnaires assessing pain, satisfaction and other quality of life indicators.

6. **STUDY POPULATION:** Women with POP, scheduled for minimally invasive SCP will be eligible for enrollment

i. **INCLUSION CRITERIA:** All patients must meet all the following inclusion criteria.

1. Age 21 or older

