## 2. ASSESSMENTS

### i. STUDY SCHEDULE

The timing of study is summarized in the Study Schedule.

	Screening	Surgery	Post-Operative Visits	
Visit	1	1	1	2
Month	Pre-op	0	1.5	6
Informed consent	X			
Demographics	X			
Pregnancy	X			
Efficacy				
POPQ	X		X	X
Procedure length		X		
Surgeon+Fellow Satisfaction (VAS)		X		
PGI-I			X	X

PFDI 20	X			
Safety				
Vaginal Wall Appearance (VAS)			X	X
Adverse events		X	X	X
Patient VAS for Pain			X	X

ii. **POP DIAGNOSIS/BASELINE POPQ:** During the preoperative visit for evaluation of POP, the provider (nurse practitioner, resident, fellow, and/or attending) will perform a POPQ exam. Each component, Aa(midline anterior vaginal wall, 3cm above external urethral meatus), Ba(most distal point of the anterior vaginal wall from the vaginal cuff or cervix, C(most distal edge of the cervix or cuff), GH(the distance from the middle of the external urethral meatus to posterior hymen), PB(posterior margin of the genital hiatus to midanal opening), tvl(greatest depth of the vagina, Ap(midline posterior vaginal wall, 3cm proximal to the hymen), Bp(the most distal point of the posterior vaginal wall from the vaginal cuff or cervix), D(posterior fornix) will be assessed. Patient will be diagnosed with POP, defined as the descent of one or more of four different anatomic structures, a) the uterus(cervix), b)the apex of the vagina (in those status post hysterectomy) c) the anterior vaginal wall, or d) the posterior vaginal wall. This is defined on exam as the POPQ points Ba, C, or Bp >0 cm beyond the hymen. In addition, uterine (Cervix) descent into at least the lower half of the vagina (defined as point C>-TVL/2) or post hysterectomy vault into the lower 2/3 of the vagina, Bothersome bulge symptoms as indicated on question 3 of the PFDI-20 form relating to 'sensation of bulging' or 'something falling out,' and desires surgical treatment for uterovaginal or vault prolapse undergoing minimally invasive SCP.

iii. **BASELINE DEMOGRAPHICS:** Patient baseline demographic information will be assessed from the electronic medical record. Information on age, BMI, ethnicity, co-morbidities, and allergies will be obtained.

iv. **INTRAOPERATIVE:** The following will be tracked: intraoperative adverse events, total surgical time, sacrocolpopexy time, mesh attachment time, type of mesh, number of attachment points

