### 3. OUTCOMES

- i. **PRIMARY OUTCOME MEASURE:** The primary efficacy outcome is the mesh to vagina attachment time using these two techniques. The timing of the mesh attachment interval was defined as beginning at the time of the initial needle or anchor being loaded on the needle driver or anchor device within the body of the patient and was introduced into the tissue of the vagina to attach the piece of mesh. As long as minimum amounts are met, here is no boundary to the amount of passes used or the amount of sutures applied. The security of the attachment of mesh will be ascertained by the attending surgeon's clinical reasoning. The time interval will end at the time the final suture is detached or anchor placed. A recording of the suture quantity utilized for each mesh attachment interval and the quantity of sutures placed in order to attach the mesh will be done. As this a time consuming component of sacrocolpopexy, a reduction in time using the anchor technique would be of considerable interest. This Mesh Attachment Interval will be recorded along with occurrence of supracervical hysterectomy as well as number of sutures or anchors placed, technical difficulties experiences, and mesh type on a de-identified document for each subject

1. **Validation of primary outcome (timing surgical procedures):** Measurement of time to complete a component of surgery has been validated in the surgical literature[16,25].
2. **Randomization/Blinding:** While intraoperative outcomes are not blinded, the examining postoperative visit provider will be blinded to group allocation. Group assignment will be performed by randomization as above.

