## 6. DATA MANAGEMENT AND ANALYSIS

1. PROCEDURES FOR DATA COLLECTION: Study participants will be closely observed by investigators to make sure that surgical appointments are set up. Data from preoperative period will be taken from the the EMR for the subject. Data for the primary outcome will be abstracted when the subject has their surgery.  
A Clinical report Form (CRF) will be used to collect history, physical examination, operation, operating times, technique, mesh attachment interval times, complications, and subsequent follow-up examination data. The investigators will input data into a pre-formatted spreadsheet. The spreadsheet will be maintained through the Kaiser Permanente San Diego research department on a password protected server and will be audited, reviewed and maintained by the investigators
  - i. Quality of Data: Data of the highest quality will be obtained from management data defined protocols for evaluating its accuracy (using source verification), completeness, accountability, and integrity.
  - ii. Completeness: the investigators will identify and complete any missing data.
  - iii. Accuracy: Errors in data will likely stem from errors in data entry. To minimize this, confirmation of data with a second source and random checks of data, and will be done. Error catching mechanisms in the Excel spread sheet and Access Database will be created with appropriate ranges and limits to help catch mistakes in data entry and allow for more accurate data entry.
  - iv. Auditing: Both sample and schedule-based auditing will be performed. Quarterly audits will be performed with random selection of 10% of the data to verify. Administrative audits will be done on a similar schedule to ensure compliance with Good Clinical Practices of the FDA.
  - v. Accountability: Accountability for data entry and data management will be with the investigators and statistical consultants.
  - vi. Integrity: mirrored hard drives, data back ups and storage on Kaiser Permanente San Diego server, will insure for data integrity.
2. ANALYSIS OF BASELINE DATA: Subject characteristics (measures and demographic information) collected at baseline will be compared across treatment groups, using either chi-square for categorical variables or t-test for continuous variables. We will examine these baseline characteristics for statistically significant differences between treatment groups, and use those that are identified for adjusted analysis correcting for these

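### Adjustment covariates are picked by baseline significance tests, and the plan does not say whether the adjusted or the unadjusted result is primary

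*SAP*

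**What the plan says.** Protocol section 6, item 2 states: "We will examine these baseline characteristics for statistically significant differences between treatment groups". The tests are chi-square or t-test. The SAP has the same text (section 1, item 2) and says it will "use those that are identified for adjusted analysis correcting for these differences in analysis of outcome variables". The primary outcome is not exempted.

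The next item in both documents, on analysis of outcomes, lists unadjusted tests only: t-test or Mann-Whitney for continuous variables, chi-squared or Fisher's exact for categorical ones. It then adds: "In addition we will use t-tests to evaluate the mean times of the different attachment approaches".

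The variables open to screening are in Protocol section 5, item 2. Under baseline demographics: "Information on age, BMI, ethnicity, co-morbidities, and allergies will be obtained". Under POP diagnosis there are nine POPQ components (Aa, Ba, C, GH, PB, TVL, Ap, Bp, D), and the entry criterion "Bothersome bulge symptoms as indicated on question 3 of the PFDI-20 form"; the schedule places the PFDI-20 at screening.

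Neither document gives a significance level for selection, the form of the adjusted model, or a statement of which result is primary.

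**The concern.** If randomisation is carried out properly, a significant baseline difference between arms is a chance finding. The test therefore says nothing useful about whether a variable needs adjustment. What matters is whether the variable predicts attachment time, and the rule does not ask that. A strong predictor that happens to be balanced is left out, and an irrelevant variable that happens to be unbalanced goes in.

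Two things are at stake. The adjusted model becomes a matter of chance, usually at a small cost in precision. And because neither result is designated primary, a reader cannot exclude that the headline result was chosen after both were known.

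**Working it through.** **1. The plan's own figures.** Inputs from SAP section 1, item 4: means 40 and 20 min, SD 20, alpha 0.05 (two-sided assumed), power 80%.
- Standardised effect: (40 − 20)/20 = 1.0.
- Normal approximation: n = 2(1.960 + 0.842)²/1.0² = 15.7, so 16 per arm. The t-distribution gives 16.71, so 17 per arm, as stated.
- Exact t-test power: 80.7% at 17 per arm, 93.4% at 25.
- Enrolment: 17/(1 − 0.30) = 24.3, so 25 per arm, as stated.

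Both figures reproduce, and both rest on an unadjusted comparison of means.

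**2. How often the rule would act.** Candidates named: 5 demographic or medical items + 9 POPQ components + PFDI-20 = 15. With independent tests at an assumed 0.05, P(at least one flag) = 1 − 0.95^k:
- k = 5: 22.6%
- k = 10: 40.1%
- k = 15: 53.7%

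If the nine POPQ points correlate at 0.5 (assumed), the simulated figure for 15 variables is 45.9–47.6%.

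**3. What the rule does to the test.** Simulation of 10,000 trials per setting, normal variables, one of them explaining R² = 0, 0.2 or 0.4 of the outcome variance (assumed). The rule adjusts for every variable with a baseline t-test p < 0.05. Monte Carlo standard error is about 0.2 points for error rates and 0.25–0.4 for power. Power entries are unadjusted/rule, in percent, at the planned effect. Disagreement is the share of those trials in which the two analyses differ on significance.

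| Variables | n per arm | R² = 0 | R² = 0.2 | R² = 0.4 | Disagreement, % |
|---|---|---|---|---|---|
| 10 independent | 25 | 93.7/92.1 | 93.3/92.7 | 93.1/92.8 | 2.3–2.8 |
| 10 independent | 17 | 80.7/76.6 | 81.0/78.4 | 80.9/79.0 | 5.8–6.5 |
| 15 independent | 25 | 93.6/91.2 | 93.7/92.1 | 93.4/92.3 | 3.3–4.0 |
| 15 independent | 17 | 80.9/75.3 | 80.7/76.1 | 80.9/77.7 | 7.9–8.6 |
| 15, POPQ correlated | 25 | 93.7/91.8 | 92.9/91.8 | 93.6/93.7 | 2.8–4.3 |
| 15, POPQ correlated | 17 | 81.2/76.8 | 81.3/77.4 | 80.6/79.1 | 6.6–10.1 |

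Subtracting these rounded entries, the change at 25 per arm runs from a gain of 0.1 point to a loss of 2.4 points. At 17 per arm the loss is 1.5 to 5.6 points.

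Type I error of the rule is 3.9–5.2% across these settings. Reporting the smaller of the two p-values gives 5.4–6.6%.

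**4. Second simulation, and what a named covariate would give.** Eight independent variables, one with correlation rho to the outcome (assumed); 20,000 null trials and 8,000 at the planned effect. Power at 17 per arm:

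| rho | Rule, % | One pre-specified prognostic covariate, % |
|---|---|---|
| 0 | 78 | 80 |
| 0.3 | 78 | 83 |
| 0.5 | 79 | 89 |
| 0.7 | 80 | 97 |

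Over 17 and 25 per arm, type I error of the rule is 3.7–5.0%, and of the smaller p-value 5.3–5.8%. Both agree with step 3.

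**5. Which n applies.** Protocol section 4, item 4: "The suture allocation sealed envelope will be opened intra-operatively once it is certain" that the attachment will be minimally invasive. Protocol section 5, item 3.i: "The time interval will end at the time the final suture is detached or anchor placed". Allocation and the primary outcome thus fall in the same operation, so later loss to follow-up does not remove the outcome. The SAP nevertheless says: "Anticipating a drop out of up to a 30% we will enroll 25 subjects in each group". The 25-per-arm rows are therefore the more relevant, and the 17-per-arm rows are the floor.

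**6. Is the unadjusted t-test a safe default?** The assumed anchor SD equals its mean, which suggests skew. With a gamma distribution (40 ± 20) against an exponential (20 ± 20), shapes assumed, over 100,000 trials the 95% interval covers 95.2% at 17 and 95.0% at 25 per arm. Power is 79.9% and 91.4%.

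**The case against.** The best counter-reading is that the unadjusted t-test is already primary: the outcomes item lists only unadjusted tests, the sample size is built on one, and adjustment appears only under baseline data. That is the most coherent reading, but it is an inference. The baseline item applies adjustment to the outcomes in general and does not label it supplementary. If the sponsor means it, one sentence settles the matter.

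The harm is also modest. At 25 per arm power stays well above 80%, the rule alone does not inflate error, and the only inflation needs selective reporting that the plan does not propose. With 5 to 15 independent variables nothing is flagged in 77% to 46% of trials, and the two analyses then coincide. All of this stands and limits the weight of the point. It does not make the rule a sound way to choose covariates.

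Three smaller objections:
- The count of 15 is approximate. Ethnicity, co-morbidities and allergies are categories or lists, whereas the simulation used normal variables. The percentages are illustrations under stated assumptions.
- If enrolment means consent, losses before the envelope is opened could bring the analysed number towards 17. That is why both sizes are shown.
- The choice between t-test and Mann-Whitney is looser wording still. For mean attachment times the t-test is named separately, and naming it as primary closes that question too.

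**Conclusion.** The concern holds. The plan sets out a definite rule that selects covariates by chance imbalance, applies it to the outcomes without exempting the primary one, and does not say which result leads. This is a defect of pre-specification and method, not an error in a stated figure: 17 and 25 per arm stand. At the planned effect the rule typically costs up to about 2 points of power at 25 per arm and up to about 6 at 17, and the two analyses disagree in roughly 2–4% and 6–10% of trials. Type I error under the rule is 3.7–5.2%, rising to 5.3–6.6% only if the better result were reported. These sizes rest on an assumed 0.05 selection threshold, the number and correlation of variables shown, and the assumed prognostic strengths. It should be corrected, but it does not threaten the design.

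**What to change.** In Protocol section 6, items 2 and 3, and the matching SAP items:
- Delete the baseline significance tests and the selection rule. Keep a descriptive baseline table.
- Name one primary analysis of attachment time. A reasonable default is the unadjusted two-sample t-test that matches the sample-size calculation, reported as a difference in means with a 95% confidence interval.
- Add, as a sensitivity analysis, a linear model with arm and one or two named covariates known before the envelope is opened. Site is an example, since Protocol section 4, item 7 mentions two; the documents do not show that it is prognostic. Making the adjusted model primary is equally acceptable if its covariates are named in advance, and it gains power if they are prognostic.
- Conditional: Protocol section 5, item 1 refers to stratification with blocks but names no factor. If a factor was used, name it there and include it in the primary model, because omitting a prognostic stratum makes the test conservative. If randomisation is blocked only, say so; nothing else changes on this point.

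The cost is wording, plus one degree of freedom per covariate or stratum term (up to about three), out of 2 × 17 − 2 = 32 or 2 × 25 − 2 = 48. The sample size does not change.
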